6.16 Treatment Discontinuation

Reasons for discontinuation of study treatment will include:

- Disease progression (Note: Patients may receive treatment after initial disease progression per RECIST v1.1 based on criteria in [Section 6.18](#))
- Initiation of alternative anti-cancer therapy including another investigational agent
- Unacceptable toxicity as defined in [Table 6-3](#) or any AE that, in the opinion of the Investigator or the Sponsor, contraindicates further dosing
- Withdrawal of consent for further treatment
- Lost to follow-up
- Patient is determined to have met 1 or more of the exclusion criteria or failed to meet all inclusion criteria AND continuing to receive IMCnyeso might constitute a safety risk. Patients who fall into this category and for whom continuation of treatment is not thought by the Investigator to pose a safety risk may, after discussion with the Sponsor Medical Monitor, continue to receive study treatment
- Pregnancy or intent to become pregnant

Information about the EOT visit and follow-up periods is provided in [Section 7.3](#).

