6.10 Dose-Escalation Decision Making

Dosing will begin with the first cohort at the starting dose of 3 mcg QW (Table 6-2). All doses administered to subsequent cohorts of patients will be determined by the SST and will be guided by the BLRM and will be subject to both the EWOC principle and the escalation rule.

Dose-escalation decisions will be made by the SST, which will consist of the Study Investigators, the Sponsor Medical Monitor, and a statistician. For each cohort, dose escalation or de-escalation decisions will be based on the SST's review of all relevant data available, from all dose levels evaluated in the ongoing study, including safety information, DLTs, all \geq Grade 2 toxicity data, PK, and pharmacodynamic data from evaluable patients (as defined in Section 6.10.2). The data and BLRM dose recommendations will be discussed and agreed upon during the dose-escalation teleconference (DETC), and all decisions will be documented in the meeting minutes and shared with all participating Principal Investigators.

If toxicity resolves following appropriate management and provided treatment discontinuation criteria are not met (see Section 6.16), patients experiencing DLTs may continue treatment with IMCnyeso only after agreement with the Sponsor Medical Monitor. With each dose cohort in Phase I, determination of the next dose to be tested in the dose escalation will be guided by the BLRM. Decision making will be based on all evaluable patients in the dose-determining set (DDS) at each cohort level (see Section 6.10.1). At each decision point, the BLRM provides an estimate of all dose levels of IMCnyeso that do not exceed the MTD and incorporates all DLT information at all dose levels for this estimation (see Section 9). In general, the next dose will have the highest chance that the true DLT rate will fall in the target interval (16%–33%) and will always satisfy the EWOC principle. In all cases, the dose for the next cohort will not exceed a 3.34-fold increase from the previous dose. Smaller dose increases may be recommended by the

Investigators and Sponsor upon consideration of all available clinical data. Further details of the BLRM including additional simulated escalation pathways are provided in [Section 13.3](#).

The estimated dose levels to be tested in this study (in the scenario that no DLT are reported) are shown in [Table 6-2](#). Actual doses will be determined using the BLRM and must be agreed upon by the SST.

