6.12 Definitions of Dose-Limiting Toxicity

A DLT is defined as an AE or abnormal laboratory value assessed as having a suspected relationship to study drug that occurs within the DLT evaluation period (Section 6.10.2), is unrelated to disease, disease progression, inter-current illness, or concomitant medications, and meets any of the criteria included in Table 6-3. Any death not clearly due to the underlying disease or extraneous causes will be considered a DLT. Other clinically significant toxicities, including a single event or multiple occurrences of the same event that lead to a dosing delay or interruption lasting > 7 days in Cycle 1, may be considered a DLT by the SST, even if not \geq Grade 3. Events meeting DLT criteria but occurring outside the DLT evaluation period may also be considered DLT by the SST. In the absence of clinically significant signs or symptoms, abnormal laboratory values that potentially meet DLT criteria must be confirmed by re-testing at least 24 hours after the initial observation.

Cytokine release syndrome will be graded based on the ASTCT 2019 criteria in [Section 13.1](#). NCI CTCAE version 4.03 will be used for all other grading. The Investigator must notify the Sponsor within 24 hours of any DLT (additional events requiring reporting within 24 hours are listed in [Section 8.5](#)).

Guidance for toxicity management is in [Section 6.15](#).

Table 6-3: Criteria for Defining Dose-Limiting Toxicities

DLTs include \geq Grade 3 AE occurring during the DLT evaluation period, with a suspected relationship to study drug, with the following modifications:	
Hematology	Grade 4 neutropenia persisting > 5 days after onset or associated with infection is a DLT \geq Grade 3 febrile neutropenia is a DLT Grade 4 thrombocytopenia or \geq Grade 3 thrombocytopenia associated with \geq Grade 3 bleeding is a DLT Grade 4 anemia is a DLT \geq Grade 3 lymphopenia in the presence of an infection indicating clinical significance is a DLT

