Cytokine release syndrome	Grade 3 cytokine release syndrome that does not resolve to \leq Grade 2 within 6 hours after onset, despite optimal medical management (eg, corticosteroid dosing), is a DLT Grade 4 cytokine release syndrome of any duration is a DLT

ALT = alanine aminotransferase; AST = aspartate aminotransferase; DLT = dose-limiting toxicity; SST = Study Safety Team; ULN = upper limit of normal.

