Grade 3	As above for Grade 2; additionally, consider systemic immunosuppressive agents (eg, methylprednisolone 1 mg/kg IV twice daily) and high-dose or multiple vasoressors as clinically indicated per institutional standards.	
Discontinue infusion immediately.
 
 • If a Grade 3 IRR improves to \leq Grade 1 within 6 hours of onset with medical management, treatment may continue with the next scheduled dose of IMCnyeso; if resolution requires $>$ 6 hours, treatment may continue with a ≥ 1 dose-level reduction • The next scheduled dose is to be delivered using a rate of infusion not to exceed 50% of rate used when the IRR occurred • Oral pre-medications (eg, 1000 mg of acetaminophen [paracetamol], 50–100 mg diphenhydramine hydrochloride or alternative antihistamine) are to be given within 60 minutes prior to the next scheduled dose of IMCnyeso • If Grade 3 IRR recurs after re-starting IMCnyeso treatment, dosing should be permanently discontinued unless the Investigator believes the overall benefit-risk favors continued treatment and following discussion and agreement with the Sponsor Medical Monitor
Grade 4	Treat as above for Grade 3 infusion-related reaction.	Permanently discontinue study treatment
Hepatic Function Abnormalities		
Grade 2	Regular monitoring of liver function tests until improving or resolved. Evaluate concurrent medications for agents that may prolong or exacerbate laboratory abnormalities. Consider IV corticosteroid therapy (eg, hydrocortisone 100 mg or the equivalent) if not improving within 72 hours.	May continue dosing.

Grade	Recommended Toxicity Management	Dose Modifications

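### Protocol Section 6.16 lists toxicity meeting the DLT table as a reason to stop treatment, while Section 6.10 and Table 6-4 allow dosing to continue after several of the same events

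*Protocol*

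**What the plan says.** Four places in the protocol bear on whether a patient with a DLT goes on receiving drug.

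- **Section 6.16.** The list opens "Reasons for discontinuation of study treatment will include" and one item is "Unacceptable toxicity as defined in" Table 6-3. A second limb of the same item covers any AE that the Investigator or Sponsor thinks rules out further dosing.
- **Table 6-3 (Section 6.12).** Its title is "Criteria for Defining Dose-Limiting Toxicities". The lead-in, which applies at Grade 3 and above, reads "Grade 3 AE occurring during the DLT evaluation period, with a suspected relationship to study drug, with the following modifications". It neither uses nor defines the term unacceptable toxicity.
- **Section 6.10.** The condition is "If toxicity resolves following appropriate management and provided treatment discontinuation criteria are not met", with a pointer to Section 6.16. The permission that follows is "patients experiencing DLTs may continue treatment with IMCnyeso only after agreement with the Sponsor Medical Monitor".
- **Table 6-4 (Section 6.15.2).** This sets dose modifications by toxicity and grade, including when dosing may continue, when it resumes at a lower level and when it stops for good.

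Sections 3.5 and 7.2 both say that treatment runs until the Section 6.16 criteria are met. The SAP tabulates discontinuations, interruptions and reductions (Sections 5.1, 8.2.5 and 8.6) but does not say how a DLT relates to stopping.

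**The concern.** Section 6.10 allows continuation subject to Section 6.16, and Section 6.16 points back to the DLT table. A site that starts from Section 6.16 would stop a patient whom a site starting from Table 6-4 would re-dose. In a first-in-human study that is an ambiguity about patient safety.

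It also touches reporting. Interruptions, reductions and discontinuations of dosing are a Phase I primary endpoint and a Phase II secondary endpoint (Protocol Table 4-1; SAP Sections 3.2.1 and 3.2.2). If the rule that generates them can be read two ways, part of what is counted may be the reading and not the tolerability of the drug.

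**Working it through.** No arithmetic applies. The check sets the passages side by side.

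**Step 1: does Section 6.10 work for a Table 6-3 event?**
1. A patient has an event that meets Table 6-3, so it is a DLT.
2. Section 6.10 permits continuation if the Section 6.16 criteria are not met.
3. Section 6.16 names toxicity as defined in Table 6-3, without any limit on grade, duration or resolution.
4. The event therefore meets Section 6.16, and the Section 6.10 permission falls away.

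The permission keeps some content. The text of Section 6.12 lets the Study Safety Team designate other toxicities as DLTs, even below Grade 3, for example events that delay dosing by more than 7 days in Cycle 1. These do not meet Section 6.16 through Table 6-3.

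**Step 2: does Table 6-4 agree with Section 6.16, event by event?**

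| Event | Table 6-3: a DLT if | Table 6-4 for that event | Agrees with 6.16 as written? |
|---|---|---|---|
| Grade 3 CRS | not down to Grade 2 or lower within 6 h | may continue after resolution, with a dose reduction and other conditions; no 6-hour limit | No |
| Grade 3 rash/pruritus | lasts more than 7 days | restart at a reduced level if down to Grade 1 or lower in 7 to 21 days | No |
| Grade 3 vomiting | lasts more than 3 days | next dose at a reduced level | No |
| Grade 3 infusion reaction | not down to Grade 1 or lower within 6 h | may continue at a reduced level if more than 6 h is needed | No |
| Isolated ALT/AST above 8 x ULN or bilirubin above 5 x ULN, below Grade 4 | any duration | stop by default; may resume at a reduced level if the Investigator judges that benefit-risk favors it | Only the exception conflicts |
| Grade 4 CRS, rash, infusion reaction, hepatic | DLT | permanent stop | Yes |

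The CRS entry in Table 6-3 begins "Grade 3 cytokine release syndrome that does not resolve to" Grade 2 or lower, so CRS that stays at Grade 3 past 6 hours is plainly a DLT, and the Grade 3 CRS row of Table 6-4 does not separate it from shorter events.

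The infusion reaction row needs care. The words "treatment may continue with the next scheduled dose of IMCnyeso" belong to the branch in which the reaction settles within 6 hours. That event is not a DLT and there is no conflict. The conflict lies in the clause that follows, for reactions needing more than 6 hours.

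**Step 3: what does the rest of the protocol suggest?** Section 6.10.1 lets a patient move to a higher dose cohort after at least 3 cycles, provided there has been no DLT. That condition would have little purpose if patients with a DLT always stopped.

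**Step 4: which periods are covered?** Table 6-3 is tied to the DLT evaluation period, 28 days under Section 6.10.2. Section 6.16 does not say whether the same toxicity in a later cycle counts as unacceptable.

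**The case against.** Several points on the other side carry weight.

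- **Section 6.16 may only list reasons to be recorded.** It says what reasons will include, whereas firm stops elsewhere use stronger language. This is arguable, but Sections 3.5, 6.10 and 7.2 all treat its content as criteria. The progression and eligibility items also carry explicit exceptions, and the toxicity item has none.
- **The citation may be a slip.** Other cross-references in the protocol are misdirected: Section 6.4 sends pre-medication to 6.12, although the content is in 6.13, and Section 7.4.3 sends RECIST to 13.1, although it is in 13.2. A slip is plausible but cannot be established from the documents, and it would need correcting anyway.
- **There is a central control.** Every DLT must be notified to the Sponsor within 24 hours, and Section 6.10 requires Medical Monitor agreement before dosing goes on. This stands, and it limits how far sites can diverge.
- **The main Phase I decision is not affected.** Under Section 6.10.2 a patient with a DLT in the evaluation period is evaluable whether or not dosing continues. The SAP (Section 4) tests no formal hypotheses. This also stands.
- **Nothing had happened by the reported data cut.** Section 1.4 reports no DLT and no AE leading to discontinuation in 15 treated patients as of 22 January 2020. The issue was prospective at that point, although SAP Table 1 shows escalation going on to a planned 30-100-300 mcg cohort.

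**Conclusion.** The inconsistency is real and lies in the current text. For DLTs that meet Table 6-3, Sections 6.10 and 6.16 cancel each other. Table 6-4 departs from Section 6.16 for four prolonged Grade 3 toxicities and, by way of an exception, for high isolated liver test elevations.

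A reader might infer more than this, and the documents do not support it:

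- *That every DLT forces a stop, so the Section 6.10 permission can never apply.* DLTs designated only under the text of Section 6.12 fall outside Table 6-3, and the permission can still operate for them.
- *That every patient with a DLT-type event is caught in the conflict.* For Grade 4 CRS, rash, infusion reaction and hepatic events, Table 6-4 and Section 6.16 agree.
- *That the endpoint is distorted.* The documents show only that descriptive counts of discontinuations and reductions could partly reflect which section was followed. No size can be put on this, because the documents give no rate for these events and no rate of divergent handling.

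The conclusion assumes that Section 6.16 sets criteria, as Sections 3.5, 6.10 and 7.2 treat it. If it were only a list of recordable reasons, the cross-reference to Table 6-3 would still leave unacceptable toxicity undefined. This is an internal inconsistency that bears on patient safety and should be corrected.

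**What to change.** Reconcile Sections 6.10 and 6.16 and Tables 6-3 and 6-4, including the Table 6-3 cross-reference in Section 6.16, so that one statement says how an event meeting Table 6-3 relates to treatment discontinuation. The statement should also say whether it applies after the DLT evaluation period. Which events stop treatment and which allow it to resume is a clinical decision for the sponsor, and none is proposed here.

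The cost is wording at the next protocol amendment. It needs no change to the sample size, the dose-escalation model or the planned tables.

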6.17 Replacement of Patients

During Phase I, any patient deemed not DLT-evaluable (see [Section 6.10.2](#)) may be replaced according to the guidelines for Phase I dose escalation, to achieve the minimum number of DLT-evaluable patients.

6.18 Treatment Past Disease Progression

Clinical evidence suggests that a minority of patients treated with immunotherapies will derive clinical benefit after an initial assessment of PD. For patients in this study, if initial PD based on RECIST v.1.1 occurs, treatment may continue according to the protocol-specified regimen provided all of the following criteria are met:

- Absence of signs or symptoms indicating clinically significant disease progression
- No decline in ECOG performance status

- No associated impending threat to vital organ function (eg, cord compression, liver function) or indication for immediate palliative therapy (eg, radiation for cord compression)

Patients continuing treatment beyond the initial protocol-specified RECIST v.1.1 progression must provide separate consent to continue IMCnyeso treatment. Disease assessments will continue to be performed according to the schedule in Table 7-2. The size of any new, measurable lesions is to be reported in the eCRF.

Patients treated beyond initial disease progression who experience further progression, defined as an additional ≥ 5 mm increase in tumor burden (sum of diameters of both target and new lesions) and/or identification of additional new lesions, at least 4 weeks after the initial PD assessment ([Seymour, 2017](#)), must permanently discontinue study treatment.

6.19 Study Discontinuation

The reasons for discontinuing individual patients from further participation the study include:

- Patient death
- Patient lost to follow-up
- Patient withdraws consent for any further participation in the study including further participation in Survival Follow-Up
- End of the study is reached (see [Section 3.6](#))

6.20 Overdose

No antidote is known for IMCnyeso nor has it been defined what constitutes an overdose. However, inadvertent incorrect dosing, such as administration of a higher dose than stated in the protocol, should be rigorously monitored for potential (serious) adverse reactions. Patients experiencing toxicity upon incorrect dosing or overdosing must receive adequate, supportive care as indicated by the symptoms observed, which will generally include IV corticosteroid therapy, at the discretion of the treating physician. Patients must be followed until full recovery or confirmed stabilization of the event.

7 STUDY SCHEDULE AND ASSESSMENTS

7.1 Pre-Screening and Screening Period Schedule

All patients will be given both a written and verbal description of the study and allowed adequate time to ask questions and decide whether they want to participate. The Investigator (or an appropriate delegate at the Investigator Site) will obtain written consent from each patient prior to commencing any study-related activities or assessments.

Pre-Screening activities may begin once a patient has signed the study IRB/IEC-approved Pre-Screening ICF. During Pre-Screening the patient's HLA-A*02:01, NY-ESO-1, and LAGE-1A status will be determined to establish patient eligibility. Once confirmed HLA-A*02:01-positive **and** NY-ESO-1- and/or LAGE-1A-positive, the patient will be invited to take part in the full study and provided with the main study information sheet.

There is no window for completion of the Pre-Screening activities. Pre-Screening may be performed while the patient is still on another anti-cancer treatment, prior to experiencing disease progression.

Screening must be completed within 21 days of C1D1; baseline radiological evaluations must be performed within 28 days prior to C1D1. Laboratory and radiological assessments performed as part of standard of care prior to signing the ICF may be used if performed within the Screening window. Screening assessments must be repeated if performed outside of the specified Screening window. Patients may re-screen after abnormal labs or symptoms are corrected or treated, but these should first be discussed and agreed with the Sponsor.

The schedule of assessments for Pre-Screening and Screening is shown in [Table 7-1](#).

Table 7-1: Schedule of Pre-Screening and Screening Assessments

Procedure	Pre-Screening	Screening
Days (relative to first dose)		-21 to -1
Informed consent	X	X
HLA-A*02:01 testing	X	
NY-ESO-1 / LAGE-1A testing (archival or new biopsy)	X	
Demography		X
Inclusion/exclusion criteria		X
Medical history and cancer history		X
Prior anti-cancer therapy		X
Prior/concomitant medications		X
Adverse events		X
Safety Assessments		
Complete physical examination		X
Height and weight		
ECOG performance status		X
Vital signs (body temperature, pulse, respiratory rate, blood pressure, and oxygen saturation)		X
12-lead ECG (triplicate)		X
Hematology panel		X
Chemistry panel		X
Coagulation		X
Urinalysis		X
Thyroid function		X
Serum pregnancy test (women of childbearing potential)		X
Serum FSH test (if required to confirm non-childbearing potential)		X
CT/MRI scans for tumor evaluation		X
[REDACTED]		
Tumor biopsy (required for \geq 10 patients in Phase II, optional for all other patients)		X
[REDACTED]		

CT = computed tomography; ECG = electrocardiogram; ECOG = Eastern Cooperative Oncology Group; FSH = follicle-stimulating hormone; HLA = human leukocyte antigen; LAGE-1A = L antigen family member-1 isoform A; MRI = magnetic resonance imaging; NY-ESO-1 = New York esophageal squamous cell carcinoma-1.

Pre-Screen Failures: Any patient who signed the Pre-Screen ICF but failed to sign the Main Study ICF and proceeded with Screening for any reason, will be considered a Pre-Screen failure. The histologic diagnosis, HLA-A*02:01 result and tumor antigen screening (NY-ESO-1 and LAGE-1A) results will be collected for all Pre-Screen failure patients. No other data will be entered in the eCRF.

Screen Failures: Any patient who signed the Main Study ICF, but failed to start treatment for any reason, will be considered a screen failure. The demographic information and reason for screen fail must be completed for screen failure patients. No other data will be entered into the eCRF unless the patient experienced any AEs during Screening, which would be reported in the usual manner via eCRF AE page (see [Section 8](#)).

7.2 Treatment Period Schedule

The treatment period starts with Day 1 of Cycle 1 (C1D1). A treatment cycle is defined as 28 days for the purposes of scheduling procedures and evaluations.

Any assessments required on C1D1 that are also performed as part of Screening do not need to be repeated on C1D1 if the data were obtained 72 hours prior to the first dose of study treatment. For subsequent visits, pregnancy testing may be performed up to 72 hours prior to dosing and other safety assessments may be performed up to 24 hours prior to dosing.

During the study visits, all tests and/or procedures should occur on schedule whenever possible. A visit window of ± 7 days (with a minimum of 7 days between doses of IMCnyeso) is allowed unless otherwise indicated in the protocol. If study drug infusions are delayed, the assessments associated with those infusions should be rescheduled accordingly. However, the timing of protocol-specified radiological assessments should be calculated in weeks using C1D1 as reference and should not be adjusted because of delays in treatment.

Assessments required during the treatment period are presented by visit in [Table 7-2](#). For patients receiving IPE, follow the alternate Cycle 1 schedule provided in [Section 13.4](#). Assessments marked “X” should be performed prior to dosing. Assessments that are to be performed at multiple timepoints are marked with the number of timepoints (including optional timepoints, if applicable) for the visit (eg, 2 \times is twice) and details of the timepoints are provided in the footnote. Additional details regarding the assessments are provided in [Section 7.4](#). Please refer to [Section 6](#) for dosing details. Patients will continue treatment until they meet criteria for discontinuation, as described in [Section 6.16](#).

Table 7-2: Schedule of Treatment Period Assessments

Procedure	Cycle 1						Cycle 2				Cycle 3				Later Cycles			
Day of Cycle	1	2	8	9	15	22	1	8	15	22	1	8	15	22	Visits on Days 1, 8, 15, and 22			
Adverse events	X	X	X	X	X	X	X	X	X	X	X	X	X	X		X		
Concomitant medications	X	X	X	X	X	X	X	X	X	X	X	X	X	X		X		
Safety Assessments																		
Complete physical examination	X																	
Abbreviated physical examination			X		X	X	X	X	X	X	X	X	X	X		D1 of each cycle		
Weight	X						X				X						D1 of each cycle	
Vital signs	~14x	~14x		3x	3x	3x	3x	3x	3x	3x	3x	3x	3x	3x		3x each dosing day		
12-lead ECG (single)	2x						2x				2x					2x on C4D1, C5D1, and C6D1		
ECOG performance status	X											X					D1 of each cycle	
Hematology panel	X	X	X	X	X	X	X	X	X	X	X		X				D1 of each cycle	
Chemistry panel	X		X		X	X	X	X	X	X	X		X				D1 of each cycle	
Thyroid function	X						X				X							
Urine pregnancy test (women of childbearing potential)	X						X				X						D1 of each cycle	
PK and Immunogenicity																		
Pharmacokinetic sampling	8x	3x	8x	X	4x	4x	2x		2x		2x		2x			2x on D1 of odd-numbered cycles		
Immunogenicity sampling	X		X		X		X				X						D1 of odd-numbered cycles	
Disease Assessment																		
CT/MRI scans and disease assessment												X				Q8W to W40 (C3, C5, C7, C9, C11), then Q12W (C14, C17, etc)		
Tumor biopsy	Between C1D9 and C1D16 (required for ≥ 10 patients in Phase II, optional for all other patients) Optional for all patients at time of progression																	

IMCnyeso administration	X		X		X	X	X	X	X	X	X	X	X	X	D1, D8, D15, and D22 of each cycle
-------------------------	---	--	---	--	---	---	---	---	---	---	---	---	---	---	------------------------------------

AE = adverse event; C#D# = Cycle # Day #; [REDACTED]; CT = computerized tomography; ECG = electrocardiogram; ECOG = Eastern Cooperative Oncology Group; EOI = end of infusion; hr = hour(s); min = minutes; MRI = magnetic resonance imaging; [REDACTED]; PK = pharmacokinetics; Q#W = every # weeks; [REDACTED]; W = week.

ECG assessments are to be done pre-dose and within 1 hour of EOI on indicated days.

Vital signs (body temperature, pulse, respiratory rate, and blood pressure; in addition, oxygen saturation should be collected for \geq first 3 cycles of treatment) are to be assessed at the following timepoints:

- C1D1/C1D2 and C1D8/C1D9: pre-dose (within 2 hours), EOI (within 15 min), every 2 hours (\pm 15 min) through 12-hour post-EOI, every 4 hours (\pm 30 min) until discharge
- All other doses: pre-dose (within 2 hours), EOI (within 15 min), and 1-hour post-EOI (\pm 15 min)

Pharmacokinetics samples are to be collected at the following timepoints:

- C1D1 and C1D8: pre-dose (within 2 hours), EOI (within 15 min), 1-hour post-EOI (\pm 15 min), 2-hour post-EOI (\pm 15 min), 4-hour post-EOI (\pm 15 min), 6-hour post-EOI (\pm 30 min), 8-hour post-EOI (\pm 1 hr), and 12-hour post-EOI (\pm 3 hr)
- C1D2: 24-hour post-EOI (\pm 4 hr), 36-hour post-EOI (optional, \pm 4 hr), and 48-hour post-EOI (optional, \pm 4 hr)
- C1D9: 24-hour post-EOI (\pm 4 hr)
- C1D15 and C1D22: pre-dose (within 2 hours), EOI (within 15 min), 8-hour post dose (\pm 1 hr), and 12-hour post-EOI (optional, \pm 3 hr)
- C2D1, C2D15, C3D1, C3D15, and D1 of subsequent odd-numbered cycles: pre-dose (within 2 hours), EOI (within 15 min)
- An unscheduled PK sample should be collected just after an ECG performed due to any unexpected cardiac signal

Central lab cytokine testing samples are to be collected at the following timepoints:

- C1D1 and C1D8: pre-dose (within 2 hours), 4-hour post-EOI (\pm 15 min), 8-hour post-EOI (\pm 1 hr), and 12-hour post-EOI (\pm 3 hr)
- C1D2 and C1D9: 24-hour post-EOI (\pm 4 hr)
- C1D15, C1D22, C2D1, and C3D1: pre-dose (within 2 hours) and 4-hour post-EOI (\pm 15 min)
- Additional samples may be collected if a patient has suspected CRS. Recommended timepoints are < 5 hours and 1 week after occurrence of the AE

